1.3. Benefit/Risk Assessment

Considering the significant unmet need for safe and effective, orally administered treatments for UC, etrasimod may potentially provide therapeutic benefit via S1P receptor modulation.

Adverse events that have been reported with S1P receptor modulators include bradycardia at the first dose or atrioventricular (AV) block, macular edema, hypertension, headache, cough, dyspnea, back pain, influenza, and diarrhea.

Safety and tolerability of etrasimod has been evaluated in Phase 1 studies with healthy adult participants at single doses up to 5 mg and repeat doses up to 4 mg once daily. Repeated doses of 2 mg have been evaluated in Phase 2 studies of participants with moderately to severely active UC (refer to the current edition of the IB). Etrasimod was found to be safe and well tolerated in these studies, with no clinically significant safety concerns with respect to vital signs, electrocardiograms (ECGs), pulmonary function tests (PFTs), ophthalmoscopy, or clinical laboratory tests. Etrasimod produced a dose-dependent sustained decrease in total lymphocyte count, which is expected given etrasimod's mechanism of action. Lymphocyte counts were within normal limits by 7 days after the last dose.

A Japanese/Caucasian ethnobridging pharmacokinetic (PK) and pharmacodynamic (PD) study (Study APD334-109) was conducted that demonstrated etrasimod 1 mg and 2 mg once-daily dosing regimens were safe and generally well tolerated by both Japanese and Caucasian participants. In that study, single and multiple dose etrasimod (1 mg and 2 mg) mean exposure (maximum observed plasma or serum concentration [C_{max}] and area under the plasma concentration-time curve [AUC]) were slightly to moderately higher in Japanese participants compared to Caucasian participants, but this was attributable to differences in body weight rather than ethnicity. No differences were observed in absolute lymphocyte counts (ALCs) between Japanese and Caucasian participants following multiple dose administration of etrasimod and levels returned to near baseline during the 7-day washout period. Additionally, there were no clinically relevant first-dose heart rate (HR) differences.

Detailed information regarding the known and expected benefits and risks and reasonably expected adverse events of etrasimod can be found in the IB, which serves as the single reference safety document for this study.

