 - Screening or Week 0/Day 1 pre-randomization vital signs (taken in the sitting position) with a HR $<$ 50 bpm OR systolic blood pressure (BP) $<$ 90 mm Hg OR diastolic BP $<$ 55 mm Hg. Vital signs may be repeated up to 3 times during a visit to confirm abnormal readings
 - Screening or Week 0/Day 1 pre-randomization ECG with PR interval $>$ 200 ms or Fridericia's corrected QT interval (QTcF) \geq 450 ms in men or \geq 470 ms in women
 - Start, stop, change or planned change in dosage of any anti-arrhythmic drugs (Class I to IV) \leq 1 week before screening or within 1 week before or after randomization
9. Forced expiratory volume at 1 second (FEV₁) or forced vital capacity (FVC) $<$ 70% of predicted values and FEV₁/FVC ratio $<$ 0.70 at screening
10. Uncontrolled diabetes as determined by hemoglobin A1c (HbA1c) $>$ 9% at screening, or participants with diabetes with significant comorbid conditions such as retinopathy
11. History of macular edema or retinopathy
12. History of active tuberculosis (TB), history of untreated or inadequately treated latent TB infection, active or latent TB infection at screening (refer to [Appendix 2](#) for details on TB screening requirements and interpretation of test results). The following are EXCEPTIONS to this exclusion criterion:
 - Participants with latent TB, who have been ruled out for active TB, have completed an appropriate course of TB prophylaxis treatment per national/local medical guidelines or WHO guidelines, have a chest radiograph without changes suggestive of active TB infection, and have not had recent close contact with a person with active TB are eligible to enroll in the study. It is the responsibility of the Investigator to verify the adequacy of previous TB treatment and provide appropriate documentation of treatment compliance
 - Participants diagnosed with latent TB at screening, ruled out for active TB and received at least 4 weeks of an appropriate TB prophylaxis regimen may be rescreened for enrollment. Participants will complete their prophylactic regimen during the trial
13. A clinically significant active infection (eg, serious and/or atypical) \leq 28 days prior to randomization, required IV medication \leq 14 days prior to randomization, or that may worsen (in

the opinion of the Investigator) if the participant is treated with a drug having immunosuppressant effects (ie, etrasimod). Fungal infection of nail beds is allowed.

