9.4.2.1.1. First Dose Cardiac Monitoring

In-clinic cardiac monitoring, of at least 4 hours, will occur on Day 1 and will include the following (Table 2):

- Full baseline vital signs (HR, systolic and diastolic BP, body temperature, and respiratory rate) and a 12-lead ECG (taken with the participant in the supine position) will be assessed pre-randomization.
- After the first dose of study treatment on Day 1, participants must remain under observation in the clinic for at least 4 hours.
- At Hours 1, 2, and 3 (\pm 15 minutes) postdose, the HR and systolic and diastolic BP will be assessed with the participant in the sitting position, with the time recorded. If the participant has an HR $<$ 50 bpm or if cardiovascular symptoms develop, then the participant should remain closely monitored, including 12-lead ECGs as clinically indicated, until the Hour 4 discharge assessment.
- At the Hour 4 (\pm 15 minutes) discharge assessment, HR and systolic and diastolic BP will be assessed with the participant in the sitting position and a 12-lead ECG (with the participant in the supine position) will be performed. Participants may be discharged from the clinic after the 4-hour assessment if they meet the criteria described in [Table 3](#). Participants not meeting the discharge criteria will require extended monitoring as described below.
- Participants experiencing a clinically relevant treatment-related symptomatic event (eg, chest pain, dizziness, palpitations, or syncope) associated with reduction of the HR or clinically relevant 12-lead ECG changes at any time during the 4-hour monitoring period must be discontinued from treatment ([Table 4](#)).

Table 2: Procedures to be Performed During the Monitoring Period

Procedure	Predose	Hours 1, 2, 3 Postdose ^a	Hour 4 Postdose ^a
Blood pressure and heart rate ^b	X	X	X
12-lead ECG	X		X
Assess discharge criteria			X

^a Measurements may be taken \pm 15 minutes of the scheduled time.

^b Heart rate is based on vital signs.

ECG, electrocardiogram

Table 3: Discharge Criteria After Cardiac Monitoring

Participants will be released from the clinical site after dosing on Day 1 (but no sooner than 4 hours postdose) when they fulfill the following discharge criteria:
• Heart rate \geq 50 bpm or no more than 10 bpm lower than the predose (baseline) value
• No evidence of second-degree AV block or higher
• No cardiac symptoms (eg, chest pain, dizziness, palpitations, lightheadedness, shortness of breath, or syncope)

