#### 18.1.5. TEAEs of Special Interest

Categories of Targeted Medical Events (TMEs) and a list of preferred terms associated with these TME categories were developed based on the mechanism of action of etrasimod, prior experience with other agents acting via a similar mechanism, and disease specific clinical judgment. In addition, where standard testing has been implemented to screen for potential AESI (eg, electrocardiograms, spirometry, serum transaminases, etc.), the relevant data will be reviewed to identify potential cases of AESI that investigators may not have identified and to provide quantitative data for AESIs. The proposed candidate terms will be reviewed to identify which events reflect AESI.

Treatment-emergent AESIs will be summarized by category, subcategory, and PT by descending frequency by treatment group. Categories and subcategories of TEAEs of special interest are the following:

- Cardiovascular Events
  - Bradycardia
  - AV conduction delay
  - Hypertension
- Macular Edema
- Pulmonary Disorders
  - Airflow obstruction (forced expiratory volume in 1 second [FEV1], forced vital capacity [FVC])
  - Decrease gas exchange (diffusing capacity of the lungs for carbon monoxide [DLCO])
- Infections
  - Severe infections
  - Opportunistic infections (Narrow)

Document: \quintiles.net\enterprise\Apps\sasdata\SASb\SAS\Arena\APD334\RZA28116\Biostatistics\Documenta

tion\SAP\503-Final SAP v2.0\APD334-203 SAP Final v2.0-20231120 clean.docx

Author: PPD Version Number: 2.0

Version Date: 20Nov2023

Template No.: CS\_TP\_BS016 Revision 7 Reference: CS\_WI\_BS005

Effective Date: 01Nov2021

Page 43 of 70

- Herpes simplex and herpes zoster
- Liver Injury
  - Liver transaminases elevation
  - Bilirubin elevation
- Posterior Reversible Encephalopathy Syndrome (PRES)
- Malignancies

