#### 18.4. ECG Evaluations

Electrocardiograms (ECG) are recorded on a 12-lead ECG machine and read centrally. The following ECG parameters will be reported for this study:

- HR (beats per minute [bpm])
- PR interval (ms)
- RR interval (ms)
- QRS interval (ms)
- QT interval (ms)
- QTcF interval (ms)
- Overall interpretation of ECG (Investigator's judgment):
  - Normal
  - Abnormal, Not Clinically Significant (Abnormal not clinically significant [NCS])
  - Abnormal, Clinically Significant (Abnormal CS)
- Overall interpretation of ECG (central reader):
  - Normal

Document: \quintiles.net\enterprise\Apps\sasdata\SASb\SAS\Arena\APD334\RZA28116\Biostatistics\Documenta

tion\SAP\503-Final SAP v2.0\APD334-203\_SAP\_Final v2.0-20231120\_clean.docx

Author: PPD Version Number: 2.0

Version Date: 20Nov2023

Template No.: CS\_TP\_BS016 Revision 7 Reference: CS\_WI\_BS005

Effective Date: 01Nov2021

Page 47 of 70

- Abnormal NCS
- Abnormal CS
- AV conduction abnormalities
  - First degree AV block
  - Second degree AV block type 1
  - Second degree AV block type 2
  - Third-degree AV block

The following summaries will be provided for ECG data:

- Value and change from Baseline by visit (for quantitative measurements)
- Incidence of markedly abnormal values (defined in Section 18.4.1) and AV blocks by visit
- Shift in normal/abnormal NCS/abnormal CS in the overall interpretation (by investigator) from Baseline to end
  of treatment and to the worst-case post-Baseline
- Shift in markedly abnormal categories from Baseline to post-Baseline by visit

Listings of ECG results, including first dose cardiac monitoring, and discharge criteria for first dose cardiac monitoring will be provided.

A listing of all ECG assessments over time in participants meeting markedly abnormal criteria will also be provided. For each subject, only ECG parameters ever meeting markedly abnormal criteria will be included.

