#### 18.4.1. ECG Markedly Abnormal Criteria

Markedly abnormal quantitative ECG measurements will be identified in accordance with the following predefined markedly abnormal criteria:

- Absolute values in QT and QTcF:
  - ≥ 450 ms (male) or ≥ 470 ms (female) in QTcF
  - > 500 ms in QT
- Change from Baseline in QT and QTcF:
  - > 30 ms increase from Baseline
  - > 60 ms increase from Baseline

Document: \quintiles.net\enterprise\Apps\sasdata\SASb\SAS\Arena\APD334\RZA28116\Biostatistics\Documenta

tion\SAP\503-Final SAP v2.0\APD334-203\_SAP\_Final v2.0-20231120\_clean.docx

Author: PPD Version Number: 2.0

Version Date: 20Nov2023

Template No.: CS\_TP\_BS016 Revision 7 Reference: CS\_WI\_BS005

Effective Date: 01Nov2021

Page 48 of 70

In shift tables, participants will be classified according to the binary category for each parameter and the predefined markedly abnormal criterion (ie, Markedly abnormal versus Not markedly abnormal, with Markedly abnormal defined in the footnote).

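### The SAP's markedly abnormal ECG criteria include change in uncorrected QT, which heart-rate slowing alone can move, and contain no PR category

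*SAP*

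**What the plan says.** SAP 18.4.1 defines markedly abnormal ECG values in two groups.

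- Absolute values: QTcF at or above 450 ms (men) or 470 ms (women), and uncorrected QT above 500 ms.
- Change, headed "Change from Baseline in QT and QTcF": "> 30 ms increase from Baseline" and "> 60 ms increase from Baseline".

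Each parameter and criterion is classified separately. No criterion concerns PR.

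SAP 18.4 feeds these criteria into three outputs: a table of "Incidence of markedly abnormal values (defined in Section 18.4.1) and AV blocks by visit", a shift table of the markedly abnormal categories, and a listing of participants who meet a criterion. For each participant the listing shows only the parameters that met one. Separately, 18.4 reports PR in ms, summarises value and change by visit for all quantitative ECG parameters, grades AV block from first to third degree, and lists all ECG results.

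The class effects in protocol 1.3 include "bradycardia at the first dose or atrioventricular (AV) block". Protocol 9.4.2.1.1 schedules an ECG 4 hours after the first dose. SAP 18.1.5 makes "AV conduction delay" a subcategory of special interest. Protocol 4.2 excludes anyone with "Screening or Week 0/Day 1 pre-randomization ECG with PR interval" above 200 ms. Protocol 9.9.3 sets its on-treatment action level at QTc above 500 ms.

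**The concern.** Uncorrected QT depends on heart rate. If active drug slows the heart more than placebo does, more participants on active drug will cross 30 ms in raw QT even if repolarisation is unaffected. A table row labelled markedly abnormal could then look like QT prolongation on etrasimod when it reflects only rate.

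The PR gap runs the other way. AV conduction is an ECG effect that the plan expects and follows as a special-interest category, and PR is its direct measurement. With no PR criterion, PR cannot enter the markedly abnormal incidence table, the shift table or the listing. By-visit means can hide a few large values, and the AV-block rows depend on a block having been recorded.

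**Working it through.** The plan states no figure for this, so there is nothing to reproduce. The check uses the Fridericia relation, QT = QTcF × (60/HR)^(1/3), with QTcF held constant while heart rate falls. The 30 and 60 ms limits come from SAP 18.4.1. Heart-rate falls and baseline QTcF are not in the documents; they are assumptions, shown as ranges.

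**Single participants**

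| QTcF (ms) | HR (bpm) | QT before, after (ms) | Rise (ms) | > 30 ms? |
|---|---|---|---|---|
| 420 | 75 to 60 | 389.9, 420.0 | 30.1 | yes, barely |
| 420 | 80 to 60 | 381.6, 420.0 | 38.4 | yes |
| 400 | 75 to 60 | 371.3, 400.0 | 28.7 | no |
| 400 | 70 to 55 | 380.0, 411.8 | 31.8 | yes |
| 440 | 65 to 55 | 428.4, 452.9 | 24.5 | no |

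In every row the change in QTcF is 0 ms by construction, and every final heart rate is at or above 50 bpm. Each therefore meets the heart-rate element of the protocol's Table 3 discharge criteria, which accepts 50 bpm or more, or a rate "no more than 10 bpm lower than the predose (baseline) value".

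**Fall needed to cross a limit t.** From starting rate h0 with starting QT0, the fall is h0 − 60 × (QTcF/(QT0 + t))^3. Over QTcF 380-440 ms and h0 65-80 bpm:

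- t = 30 ms: from 11.9 bpm (QTcF 440, h0 65) to 17.7 bpm (QTcF 380, h0 80).
- t = 60 ms: from 21.1 to 30.5 bpm at the same two corners.

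A fall of exactly 10 bpm never reaches 30 ms in this range; the largest rise is the 24.5 ms in the last row.

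**Groups.** Those are individual thresholds. A smaller mean fall still pushes part of the distribution past them. Simulation with 400,000 participants per scenario assumed baseline HR mean 74, SD 10; baseline QTcF mean 420, SD 15; and QTcF change mean 0, SD 10, that is, no drug effect on QTcF.

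| Mean HR fall (bpm) | Raw QT > 30 ms, SD of HR change 5 | Raw QT > 30 ms, SD of HR change 8 |
|---|---|---|
| 0 | 1.7% | 5.9% |
| 5 | 8.3% | 15.2% |
| 10 | 25.7% | 31.3% |

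With mean QTcF 400 the figures are slightly lower: 1.5% and 5.4%, 7.4% and 14.0%, 23.3% and 29.2%. QTcF > 30 ms stays near 0.1% throughout, as it must: P(Z > 30/10) = 0.13%. Raw QT > 60 ms is rarer: at SD 8 and mean QTcF 420, about 1.5% with a 5 bpm mean fall and 5% with 10 bpm.

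On the planned 32 per arm, the SD 8 column corresponds to 32 × 0.059 = 1.9, 32 × 0.152 = 4.9 and 32 × 0.313 = 10.0 participants. Actual arms will be smaller, since SAP 3.1 and 7 say the study stops early.

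**Does the 4-hour ECG count?** SAP 6.4 takes the earliest ECG of a day for by-visit analyses, which on Day 1 would be the predose one. SAP 6.3, however, brings all measurements into summaries of abnormalities and worst post-baseline values. The 4-hour ECG therefore counts here.

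**The 500 ms category.** Raw QT of 500 ms equals a QTcF of 500/(60/HR)^(1/3): 470.5 ms at 50 bpm, 500 ms at 60 bpm and 526.4 ms at 70 bpm. The SAP's raw-QT limit and the protocol's QTc level coincide only at 60 bpm, and no planned table counts QTcF above 500 ms.

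**The case against.** The strongest reply is that a careful reader would not be misled. QT and QTcF are classified separately, ECG heart rate is reported, and SAP 18.5 gives detailed Day 1 heart-rate displays. A raw-QT flag without a QTcF flag, beside a lower heart rate, can be interpreted. This stands for the tables. It is weaker for the markedly abnormal listing, where a participant flagged on raw QT alone appears without the QTcF and heart rate that explain the flag; those values must be found in the full ECG listing.

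A second reply is that conduction is already covered: PR value and change are summarised by visit, AV blocks are tabulated from first degree upward, ECGs are read centrally, and SAP 18.1.5 plans a review of ECG data for cases investigators missed. This also stands. A reader might infer that the plan yields no numeric AV-conduction signal; 18.4 shows otherwise. Only a categorical PR outlier count is missing, with its shift row and listing entry. A PR row would partly overlap the first-degree block row, but it would not depend on a block being recorded.

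Third, the size depends on assumed values. That is right, and it is why ranges are given.

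Finally, no statistical comparison of safety data is planned unless otherwise specified (SAP 18), and protocol 10.12.2 asks only that outlier ECG results be tabulated, without naming parameters. This limits the consequence to presentation.

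**Conclusion.** The point holds in a limited form. The raw-QT change categories are confounded by heart rate and can separate the arms with QTcF unchanged. Under the stated assumptions, the share above 30 ms rises from about 2-6% with no mean fall in heart rate to 8-15% with 5 bpm and 26-31% with 10 bpm. A reader might infer that the table will show a false QT signal on etrasimod. The documents do not support that: they give no heart-rate effect for etrasimod in this population, so the difference could be small or absent.

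The PR gap is confined to the categorical outputs. The mismatch at 500 ms between SAP 18.4.1 and protocol 9.9.3 is plain on the text and needs reconciling. Severity is minor, because the display is descriptive and the underlying values are all listed.

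**What to change.** In SAP 18.4.1:

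1. Restrict the > 30 and > 60 ms change categories to QTcF. Keep raw QT in the value and change-from-baseline table.
2. Add a post-baseline PR > 200 ms category to the incidence table, shift table and markedly abnormal listing. This borrows the protocol's entry limit as a tabulation threshold only. Because entry is barred above it, the row should start at or near zero in every arm.
3. Reconcile the > 500 ms category, which is on raw QT, with protocol 9.9.3, which refers to QTc. The sponsor should state which parameter the table is meant to count.

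QT, QTcF and PR are already reported parameters, so the cost is SAP wording and revised table and listing shells. What is lost is the raw-QT change outlier rows.

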#### 18.5. Vital Signs

The following vital signs measurements will be reported for this study:

- Systolic Blood Pressure (mmHg)
- Diastolic Blood Pressure (mmHg)
- Heart Rate (bpm)
- Respiratory Rate (resp/min)
- Temperature (°C)
- Weight (kg)
- Height (cm) (Screening only)

The following summaries will be provided for vital signs data:

- Value and change from Baseline by visit
- Value and change from predose on Day 1 (as reported on the eCRF) by timepoint
  - Value and change from predose to minimum postdose heart rate on Day 1 will be included in the same table
- Incidence of markedly abnormal values (defined in Table 4) by visit
- Listing of participants meeting markedly abnormal criteria
- Incidence of minimum heart rate on Day 1 by postdose timepoint (1, 2, 3, 4, and > 4 hours postdose, and Day 1 overall) and heart rate interval (≥ 65, 60 to 64, 55 to 59, 50 to 54, 45 to 49, 40 to 44, < 40 bpm)
  - If minimum heart rate is attained at multiple postdose timepoints, only the earliest timepoint will be counted in this incidence summary.
- Time to minimum heart rate on Day 1 by planned hourly timepoint (if minimum heart rate is attained at multiple postdose timepoints, only the earliest timepoint will be counted).
  - Actual time elapsed from first dose to minimum heart rate on Day 1 will also be summarized using descriptive statistics (n, mean, SD, median, minimum, and maximum) in the same table.

Document \\quintiles.net\enterprise\Apps\sasdata\SASb\SAS\Arena\APD334\RZA28116\Biostatistics\Documenta tion\SAP\503-Final SAP v2.0\APD334-203 SAP Final v2.0-20231120 clean.docx

Version Number:

Version Date: 20Nov2023

2.0

Template No.: CS\_TP\_BS016 Revision 7 Reference: CS\_WI\_BS005

Effective Date: 01Nov2021

PPD

Author:

Page 49 of 70

- Line plots for mean value and mean change from predose on Day 1, up to 4 hours postdose by parameter and timepoint (systolic blood pressure, diastolic blood pressure, and heart rate)
- Line plots for mean value and mean change from Baseline by parameter and visit (systolic blood pressure, diastolic blood pressure, heart rate)

Listings of all vital signs, including first dose cardiac monitoring, and discharge criteria for first dose cardiac monitoring will be provided. A listing of vital signs assessments over time in participants meeting a markedly abnormal criterion will also be provided. For each subject, only the parameters with at least one markedly abnormal criterion satisfied will be included.

For participants with extended monitoring or re-monitoring, a listing of systolic blood pressure, diastolic blood pressure, heart rate values, and change from predose in all parameters on Day 1, Day 2, and any re-monitoring visit will be provided.

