9.4. Randomization/Treatment Period

9.4.1. Week 0/Day 1: Pre-randomization

At the Week 0/Day 1 visit (Table 6), prior to randomization, a 12-lead ECG in the supine position and resting vital signs in the sitting position (HR, systolic and diastolic BP, body temperature, and respiratory rate) will be collected. Caffeine and/or nicotine are not permitted within 30 minutes prior to BP measurements.

Participants with the following must not be randomized and should be considered screen failures:

- Sitting vital sign assessment: HR < 50 bpm OR systolic BP < 90 mm Hg OR diastolic BP < 55 mm Hg
- 12-lead ECG showing a second-degree or third-degree AV block, periods of asystole > 3 seconds, PR interval > 200 ms, or QTcF \geq 450 ms (men) or QTcF \geq 470 ms (women).

All predose 12-lead ECGs should be obtained prior to blood sample collection.

Participants who continue to meet all eligibility criteria will be randomized as outlined in Section [6.4](#).

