10.11. Safety Endpoints

- Incidence and severity of adverse events
- Incidence and severity of laboratory abnormalities, and change from baseline in laboratory values (to include hematology, serum chemistry, coagulation, and urinalysis)
- Incidence of clinically significant vital sign abnormalities and changes from baseline

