#### 18.3.1. Safety Laboratory Evaluations

Hematology, serum chemistry, coagulation, and urinalysis are analysed and reported by central laboratory and sometimes by local laboratory. Results out of reference range are flagged by the performing laboratory (eg, low, high). A full list of laboratory assessments to be included in the outputs is included in Clinical Study Protocol APD334-203 Table 6.

In general, presentations will use Système international d'Unités (SI units). Quantitative laboratory measurements reported as "< X" or "> X", where X may be the lower limit of quantitation (LLQ) or the upper limit of quantitation (ULQ), respectively, will be converted to X for the purpose of quantitative summaries, but will be presented as recorded, ie, as "< X" or "> X" in the listings. For urinalysis, only pH and specific gravity are considered as quantitative tests. If local and central laboratory assessments are available from the same day, central laboratory assessments will be used in the summary as per Section 6.4.

The following summaries will be provided for laboratory data:

- Value and change from Baseline by visit (for hematology, serum chemistry, quantitative urinalysis [pH and specific gravity], coagulation, and high-sensitivity C-reactive protein [hs-CRP])
- Incidence of abnormal values according to laboratory reference ranges by visit
- Incidence of lymphocytes  $< 0.2 \times 10^9/L$ ,  $0.5 \times 10^9/L$ , or neutrophils  $< 0.5 \times 10^9/L$ ,  $1 \times 10^9/L$  at end of treatment and anytime in the study
- Shift from end of treatment to each follow-up visit in incidence of lymphocytes in normal range and in incidence of lymphocytes of at least 80% percent of Baseline, by visit (2-Week Follow-Up, 4-Week Follow-Up, and Last Follow-Up)

Document: \\quintiles.net\enterprise\Apps\sasdata\SASb\SAS\Arena\APD334\RZA28116\Biostatistics\Documenta

tion\SAP\503-Final SAP v2.0\APD334-203 SAP Final v2.0-20231120 clean.docx

Version Number: 2.0 Author: PPD

> Version Date: 20Nov2023

Template No.: CS\_TP\_BS016 Revision 7 Reference: CS WI BS005

Effective Date: 01Nov2021

Page 45 of 70

- Shift from Baseline to end of treatment according to laboratory reference range (for quantitative measurements and categorical measurements)
- Evaluation of drug-induced serious hepatotoxicity (eDISH) plots for the following laboratory assessments (using values after the first administration of study treatment):

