#### 18.5.2. Vital Signs Markedly Abnormal Criteria

Markedly abnormal quantitative Vital Signs measurements will be identified in accordance with the following predefined markedly abnormal criteria:

Table 4: Markedly Abnormal Criteria for Vital Signs

Variable	Unit	Low	High
SBP	mmHg	≤90 mmHg	> 150 mmHg
DBP	mmHg	≤50 mmHg	> 90 mmHg
Heart rate	bpm	< 40 bpm < 50 bpm < 50 bpm and decrease from predose (Baseline) of > 10 bpm at 4 hours on Day 1 or Day 2 or remonitoring visit	> 100 bpm

bpm, beats per minute; DBP, diastolic blood pressure; SBP, systolic blood pressure.

Document: \quintiles.net\enterprise\Apps\sasdata\SASb\SAS\Arena\APD334\RZA28116\Biostatistics\Documenta

tion\SAP\503-Final SAP v2.0\APD334-203 SAP Final v2.0-20231120 clean.docx

Author: PPD Version Number: 2.0

Version Date: 20Nov2023

Template No.: CS\_TP\_BS016 Revision 7 Reference: CS\_WI\_BS005

Effective Date: 01Nov2021

Page 50 of 70

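### SAP 18.5 counts high blood pressure and heart rate by visit on absolute value alone and plans no table separating participants who already met the criterion at baseline

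*SAP*

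**What the plan says.** Protocol 10.11 names as a safety endpoint "Incidence of clinically significant vital sign abnormalities and changes from baseline". SAP 18.5 serves it with "Incidence of markedly abnormal values (defined in Table 4) by visit", with "Value and change from Baseline by visit", with mean plots and with listings, among them: "A listing of vital signs assessments over time in participants meeting a markedly abnormal criterion will also be provided".

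Table 4 in SAP 18.5.2 has eight criteria. Seven are absolute values. The eighth, assessed at 4 hours on Day 1, Day 2 or a re-monitoring visit, also requires a fall: "< 50 bpm and decrease from predose (Baseline) of > 10 bpm".

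Entry excludes low values only. Protocol 9.4.1 lists as a screen failure: "Sitting vital sign assessment: HR < 50 bpm OR systolic BP < 90 mm Hg OR diastolic BP < 55 mm Hg". Exclusion criterion 8 in Protocol 4.2 has the same limits. Neither gives an upper limit for blood pressure or heart rate, and no exclusion criterion names hypertension.

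Two other SAP safety sections tabulate movement from baseline. For ECG, 18.4 plans "Shift in markedly abnormal categories from Baseline to post-Baseline by visit". For laboratory data, 18.3.1 plans "Shift from Baseline to end of treatment according to laboratory reference range". Section 18.5 has no such line.

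**The concern.** A participant who enters with DBP 94 and stays at 94 is counted as markedly abnormal at every post-baseline visit, in the same cell as one who rises from 78 to 94. The by-visit count cannot tell them apart.

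This matters most for blood pressure. SAP 18.1.5 lists hypertension as a subcategory of events of special interest, and Protocol 1.3 names it among events reported with this drug class. SAP 3.1 and 7 say the study stops early with fewer participants than planned, and SAP 18 plans no statistical comparison of arms for safety data unless otherwise specified. Readers will rely on raw counts in small arms, where one or two participants who were already hypertensive, unevenly allocated by chance, can suggest a drug effect or mask one.

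**Working it through.** The plan states no figure to reproduce here. The check sets Table 4 beside the entry limits and then illustrates the size.

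**Step 1: which criteria can be met at an eligible baseline?**

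| Table 4 criterion | Entry rule | Met at an eligible baseline? |
|---|---|---|
| SBP > 150 | no upper limit | yes |
| DBP > 90 | no upper limit | yes |
| HR > 100 | no upper limit | yes |
| SBP ≤ 90 | excluded if < 90 | only at exactly 90 |
| HR < 50 | excluded if < 50 | no |
| HR < 40 | excluded if < 50 | no; 10 bpm below the limit |
| DBP ≤ 50 | excluded if < 55 | no; 5 mmHg below the limit |
| HR < 50 with a fall > 10 from predose | excluded if < 50 | no; it also has its own baseline condition |

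Three criteria are fully exposed, one is exposed at a single value, and four are not affected.

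**Step 2: does any planned output give the split by arm?**

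- Incidence by visit: no condition on baseline status.
- Change from Baseline and mean plots: group summaries, which do not show who crossed a threshold.
- Listings: show each case over time, but are not a count.
- A Baseline row in the incidence table: the SAP does not say whether there is one. It would give group counts at baseline, not movement within participants.

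None of these gives it.

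**Step 3: chance imbalance at baseline.** Assumptions: 8% of participants meet a high criterion at baseline, and arms are smaller than the planned 32. The SAP gives no reduced number, so 16–20 is assumed. With A and B independent Binomial(n, 0.08), the quantity is P(|A − B| ≥ k), where k is the smallest whole number that is at least 0.10 × n.

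| n per arm | expected pre-existing cases (0.08 × n) | k | probability |
|---|---|---|---|
| 16 | 1.28 | 2 | 30.9% |
| 20 | 1.60 | 2 | 36.5% |
| 24 | 1.92 | 3 | 17.5% |
| 32 | 2.56 | 4 | 10.3% |

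The figures do not fall smoothly because k moves in whole participants; at 16 and 20 per arm, 10 points means two people. With prevalence varied from 5% to 20%, the probability is 20–50% at 16 per arm and 4.5–27% at 32. Each figure is for one pair of arms.

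**Step 4: how many by-visit cases were already cases?** Assumptions, with no drug effect: DBP mean 74–78, between-person SD 8–9 and within-person SD 5–6 mmHg, with baseline readings below 55 excluded. Example with 76, 8 and 6:

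- SD of a single reading = √(8² + 6²) = 10
- z = (90 − 76)/10 = 1.4, so about 8% exceed 90 at a visit
- correlation of two readings = 64/100 = 0.64
- simulated share of those above 90 at a visit who were also above 90 at baseline: about 40%

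Over the whole grid, 5–14% exceed 90 at any one visit and 35–55% of them were above 90 at baseline. With readings rounded to whole mmHg, the ranges are 4–13% and 34–54%. At mean 72 the share is lower, about 30–44%.

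**The case against.** The strongest defence is that the plan already holds the information. Listings cover all vital signs, and a separate one follows each flagged participant over time. At 4–14% per visit and 16–20 per arm, that is about one to three people per arm at any visit for DBP (0.04 × 16 ≈ 0.6 to 0.14 × 20 ≈ 2.8), which a reader can sort by hand. Randomisation balances pre-existing cases in expectation, and medical history and concomitant medication are tabulated. Pulmonary function (18.7.1) also lacks a shift table, so vital signs are not the only section without one. All of this stands and limits the harm. It still leaves no tabulated split by arm.

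Three stronger readings are tempting, and the documents do not support them.

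- *All of Table 4 ignores baseline.* Step 1 shows that four of the eight criteria are unaffected and that SBP ≤ 90 overlaps entry at one value only.
- *The SAP breaks a protocol promise.* Protocol 10.12.2 mentions shift tables, but directly after its laboratory sentences. For vital signs it promises change from baseline and the incidence of abnormal parameters, and 18.5 plans both.
- *The special-interest counts for hypertension are contaminated.* Those are treatment-emergent events, which under SAP 18.1 must start or worsen on or after the first dose. Table 4 does not define them.

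One limit of the remedy also stands. By step 4, about 45–65% of no-effect cases above 90 at a visit were not above 90 at baseline. Restricting to participants below the threshold at baseline removes pre-existing cases, not within-person variation.

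**Conclusion.** The point holds for SBP > 150, DBP > 90 and HR > 100, and marginally for SBP ≤ 90. For these, the by-visit incidence mixes abnormalities present before the first dose with those that appear afterwards, and no planned table separates them by arm. This is a gap in tabulation. It does not show a biased comparison or a wrong threshold.

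The structural finding rests on the documents alone. Its size does not: the 31–37% (16–20 per arm) and 10% (32 per arm) figures assume 8% pre-existing cases, and the roughly 35–55% share assumes the DBP distribution in step 4. The change is worth making because it costs little and the arms will be small.

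**What to change.** In SAP 18.5, add the line that 18.4 already has, "Shift in markedly abnormal categories from Baseline to post-Baseline by visit", for SBP, DBP and HR, on the Safety Set. Beside each current incidence row, add the incidence among Safety Set participants who did not meet that criterion at Baseline. Use the Safety Set only, since SAP 18 bases all safety outputs on it and the FAS groups participants by randomised rather than received treatment. Label the row as criterion not met at Baseline rather than as treatment-emergent, because it will still contain within-person variation.

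Keep the current rows, thresholds and listings. The cost is one extra shift table and a few rows from data already collected.
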